8.4 Preparation, Dosage and Administration

Prescribing and Dispensing

The allocated treatment will be dispensed by the local trial pharmacist after receiving a study-specific prescription.

Each participant will receive the treatment divided between two bottles as follows:

- 1 bottle containing two days worth of treatment for the day pre-op and the day of surgery
- 1 bottle containing 12 days worth of medication for ongoing treatment post-operatively

Both bottles will be packaged into a fitted carton. Participants will be instructed to use the 'two-day' bottle first and to bring all of their medication with them when attending for surgery. In the event that doses are taken pre-operatively from the 'two-day' bottle as planned and, if surgery is cancelled, a replacement prescription will be issued for administration at the rescheduled surgery. In the event that a participant attends for surgery but does not bring their medication with them, a replacement prescription will be issued.

Administration of IMP and Comparator

The first two doses will be administered in the 24 hours prior to planned surgery. The participant will take the medication for 14 days in total.

Levetiracetam – taken orally, 500mg (taken as 2 x 250mg over-encapsulated capsules), twice a day (AM and PM), taken at approximately the same times each day, spaced as close to 12 hours apart as possible.

Placebo – taken orally, 2 over-encapsulated capsules, twice a day (AM and PM), taken at approximately the same times each day, spaced as close to 12 hours apart as possible.

Example dose regime for a patient with surgery scheduled for a Tuesday:

Day 1: Monday: IMP or placebo taken approximately 12 hours apart e.g. 0800 hours and 2000 hours

Day 2: Tuesday (day of surgery): dose taken on morning of surgery, prior to anaesthesia. Dose taken in evening after surgery.

Days 3-14: Wednesday onwards: twice daily dosing as per Monday.

In the event of missed doses this should be recorded on the CRF and the participant should continue and complete the full treatment course. Examples for having a missed dose include:

1. Administration error
2. Participant remains intubated and ventilated after surgery and is therefore unable to take oral medication.

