10.4 Baseline Assessments

After confirming eligibility and obtaining written informed consent, baseline assessments should be completed as per the Schedule of Assessments (Section 10.7) in order to accurately complete the Baseline CRF and collect the necessary information for the trial analyses. This includes the following assessments/data:

- Medical / neurosurgical history will be reviewed and recorded on the appropriate eCRF.
- Presenting symptoms of specific interest will be collected.
- Performance status (using Karnofsky Performance Status [KPS] scale) will be assessed (see section 21.2).
- Quality of life using EQ-5D-5L questionnaire will be completed by the participant and collected.
- Resource use using Resource Use Questionnaire will be completed by the participant and collected.
- Participants will be asked about their DVLA Licence status.

Routinely collected information can be transcribed from the patient's medical notes into the eCRF once appropriate consent has been obtained. The patient's GP will be sent a letter to advise of their patient's involvement in the trial.

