10.5 Randomisation Process

Eligibility and baseline assessments will occur prior to surgery, either at the pre-admission visit or on the ward as an in-patient, typically within 2 weeks of surgery.

Once the baseline assessments are complete the participant can be randomised. Participants will be randomised via a secure (24-hour) web-based randomisation system controlled centrally by the LCTC to receive either levetiracetam or placebo in a ratio of 1:1. Randomisation can occur at any time once:

- a) Eligibility is confirmed
- b) Fully informed written consent has been appropriately documented
- c) Baseline assessments have been completed.

After completing the relevant training, designated research staff within site will be issued with a personal login username and password to access the randomisation system.

When patient consent and full eligibility are confirmed in the system, a unique trial number (randomisation number) will be displayed on a secure webpage and an automated email confirmation will be sent to the delegated pharmacy to confirm treatment allocation. Other designated personnel (e.g. randomising researcher, site PI, LCTC trial manager) will receive a separate email confirming that randomisation has taken place without revealing treatment allocation.

Randomisation: web access <https://rand.lctc.org.uk/STOPEM>

*If there are any problems with the randomisation systems contact
LCTC on [name] or via email on [contact]*

(Note that the LCTC is open 0900 – 1700, Monday – Friday, excluding public holidays)

Randomisation System Failure

In the event of a randomisation system failure, the site should contact the LCTC (Monday to Friday between 9:00 to 17:00 excluding bank holidays) to resolve the problem.

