10.7 Schedule for Assessments and Follow-up

All assessments and follow up are to be conducted in line with the Schedule of Assessments below:

Schedule of Assessments:

Procedures	Screening	Baseline ^a	1 day before surgery, continuing for a total of 2 weeks	Day of surgery	Knife-to-skin, then at 1, 4, 24 and 48 hours after knife-to-skin	Follow-Up Schedule				
						Follow-up 1: 4-6 weeks post-surgery ^c	Follow-up 2: 12 weeks (±4 weeks) post-surgery ^c	Follow-up 3: 24 weeks (±4 weeks) post-surgery ^d	Follow-up 4: 36 weeks (±4 weeks) post-surgery ^d	Follow-up 5: 52 weeks (+8 weeks) post-surgery ^c
Signed Consent Form and Patient Identifiable Data	X	X								
Assessment of Eligibility Criteria	X	X								
Medical/Neurological History	X	X								
Concomitant Medications/Anti-epileptic drugs	X	X				X	X	X	X	X
Assessment of Performance Status (using KPS scale)		X				X	X			X
Quality of Life Questionnaire – EQ-5D-5L		X				X	X			X
Resource Use Questionnaire		X				X	X			X
MRI scan	X ^b									X
Randomisation		X								
Trial intervention (IMP or Placebo) adherence			X	X		X	(X)			
Blood sample (Inflammatory Biomarker Sub-study)					(X)					
30-day morbidity and mortality assessment						X	(X) ^e			
Symptoms of possible seizures						X	X	X	X	X
Recording of Serious Adverse Reactions			X		X	X	(X)	(X)	(X)	(X)
Assessment of DVLA Licence		X								X

^aAt baseline, all procedures should be done before trial intervention

^bBaseline pre-operative MRI scan

^cClinic visit (face-to-face or video consultation)

^dTelephone consultation

^eIf not done completed at follow-up 1

Follow-up 1: 4-6 weeks post-surgery (clinic visit – face-to-face or video consultation)

This will be conducted where possible during a scheduled hospital appointment where the participants progress will be evaluated and the following information collected:

- Details of any Anti-Epileptic Drug (AED) prescribed.
- Symptoms of possible seizures reviewed.
- Performance status assessed using Karnofsky Performance Status [KPS] scale.
- Quality of life using EQ-5D-5L questionnaire (participant completed or interviewer).
- Resource Use Questionnaire will be completed and collected (participant completed or research team, if remote).
- 30-day morbidity and mortality will be collected using Landriel Ibañez classification system (see section 12.3).
- Any Serious Adverse Reactions will be recorded.

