- The participant will be asked to confirm treatment compliance, willingness to continue and be advised about the next visit.

Checks on suicidal ideation and psychosis should be made and managed clinically as per routine practice.

In patients who develop seizures after completing the 14-day course of trial treatment, any investigations/treatment will be coordinated as per usual NHS practice. Participants will not be unblinded as the study treatment has stopped and the participant will remain on study and continue follow-up for 12 months. Information about the commencement of AED will be collected.

Follow-up 2: 12 weeks (±4 weeks) post-surgery (clinic visit – face-to-face or video consultation)

This will be conducted where possible during a scheduled hospital appointment where the participants progress will be evaluated and the following information collected:

- Details of any AEDs prescribed.
- Symptoms of possible seizures reviewed.
- Performance status assessed using Karnofsky Performance Status [KPS] scale.
- Quality of life using EQ-5D-5L questionnaire (participant completed or interviewer).
- Resource Use Questionnaire will be completed and collected (participant completed or research team, if remote).
- 30-day morbidity and mortality will be collected using Landriel Ibañez classification system (*if not already collected at Follow-up visit 1*).
- The participant will be asked to confirm treatment compliance (if not confirmed at follow-up 1) confirm willingness to continue and advised about the next visit.

Checks on suicidal ideation and psychosis should be made and managed clinically as per routine practice.

Follow-up 3: 24 weeks (±4 weeks) post-surgery (telephone consultation)

This is a scheduled telephone visit and will be a discussion between the participant and a staff member.

- Details of any Anti-Epileptic Drug (AED) prescribed.
- Staff will collect details of any potential seizure symptoms.
- The participant will be asked to confirm willingness to continue and be advised about the next visit.

Follow-up 4: 36 weeks (±4 weeks) post-surgery (telephone consultation)

This is a scheduled telephone visit and will be a discussion between the participant and a staff member.

- Details of any Anti-Epileptic Drug (AED) prescribed.
- Staff will collect details of any potential seizure symptoms.
- The participant will be asked to confirm willingness to continue and be advised about the next visit.

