Grade IIa	Complication requiring intervention without general anaesthesia 
 • Dehiscent non-infected wound requiring closure under local anaesthesia • Subgaleal CSF collection (pseudomeningocele) requiring lumbar drain

Grade IIb	Complication requiring intervention with general anaesthesia 
 • CSF leak requiring surgical repair • Wound infection requiring surgical lavage / bone flap removal • Pseudomeningocele requiring external ventricular drain or shunt
Grade III	Life-threatening complication that may require management in critical care
Grade IIIa	Complication involving single organ failure 
 • Acute hydrocephalus requiring external ventricular drain or shunt • Intracranial haematoma requiring re-operation • Cerebral oedema requiring intubation
Grade IIIb	Complication involving multiple organ failure 
 • Meningitis and pneumonia (or other organ failure e.g. renal) • Intracranial hypertension and haemodynamic instability • Ischaemic stroke and pneumonia (or other organ failure e.g. renal)
Grade IV	Complication resulting in death

Process for Monitoring Seizures

Patients will be given contact details for the site research team, as well as a checklist of symptoms to look out for that might be seizures. If a patient develops any of these symptoms, they will contact the research team. The patient will be assessed by the research team to see if the symptoms are consistent with seizures.

As per routine clinical pathways, local neurology input may be required to confirm the diagnosis and commence appropriate anticonvulsant medication.

MRI scans

MRI will be performed in all participants as per routine clinical practice at baseline (pre-operatively) and 12 months. Details of imaging sequences are given in the separate MRI manual, alongside instructions on how to transfer pseudoanonymised images to The Walton Centre.

Efficacy Assessments

Details of signs and symptoms of possible seizures, and of any AED prescribed will be collected at every follow-up time point.

Safety Assessments

All participants will complete a symptoms checklist, administered by a research nurse, 4-6 weeks post-surgery (follow-up 1). This will help determine any adverse reactions specifically related to the IMP.

Quality of Life Assessments

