10.8 Intervention Discontinuation and Participant Discontinuation/Withdrawal

In consenting to the trial, participants agree to all trial activities including administration of trial intervention and treatment and follow-up assessments / visits and data collection. Every effort should be made to facilitate the completion of these for every recruited participant. If it is not possible to complete these activities (or it is deemed inappropriate) the reasons why should be documented. The following sub-sections describe the different levels of discontinuation/withdrawal.

Premature Discontinuation of Study Intervention

Participants may discontinue treatment for reasons including, but not limited to:

- Participant-led i.e. request by the participant / legal representative
- Unacceptable toxicity (see Section 11 for Adverse Event reporting)
- Intercurrent illness preventing further treatment.
- Clinician-led:
 - Any change in the participant's condition that justifies the discontinuation of treatment in the clinician's opinion.
 - Reasons of non-adherence or non-compliance with treatment or other trial procedures
 - Participant develops renal failure that is a contraindication to levetiracetam

Discontinuation from study intervention does not mean discontinuation of the study altogether, and the remaining study procedures, follow up assessment / visits and data collection should be completed as indicated in the protocol (unless consent is specifically withdrawn) prior to unblinding.

Participant Withdrawal from Follow Up

Participants are free to withdraw from follow up at any time without providing a reason, though a reason should be recorded if one is given. Those who wish to withdraw from further follow-up will have the data collected up to the point of that withdrawal included in the analyses. The participant will not contribute further data to the study and the LCTC should be informed via email to the LCTC and via completion of a Withdrawal CRF to be returned to the LCTC within 7 days.

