12.6 Time Period for Active Monitoring of Safety Events

IMPORTANT: Any safety events occurring after the end of the “active monitoring” period described below, which meet the definition of serious (see section 12.2) and are recorded for this study, must continue to be reported by sites to the LCTC in accordance with the timeframes and procedures described in sections 12.9 and 12.10. The same processes established for SARs within the active monitoring period should be followed for these events.

Active monitoring of safety events experienced by trial participants will be from the period of randomisation until completion of IMP course, plus 1 week.

Section 12.7 for more information on reporting pregnancy.

Notes on Safety Event Recording

The following events must be recorded for the purposes of the trial:

- An exacerbation of a pre-existing illness
- An increase in frequency or intensity of a pre-existing episodic event/condition
- A condition (even though it may have been present prior to the start of the trial) detected after trial drug administration
- Continuous persistent disease or symptoms present at baseline that worsens following the administration of the study/trial treatment
- Laboratory abnormalities that require clinical intervention or further investigation (unless they are associated with an already reported clinical event).

- Abnormalities in physiological testing or physical examination that require further investigation or clinical intervention
- Injury or accidents
- Pregnancy (See section 12.7 for more details)

Do not record:

- Medical or surgical procedures - the condition which leads to the procedure is the adverse event
- Pre-existing disease or conditions present before treatment that do not worsen
- Situations where an untoward medical occurrence has occurred e.g. cosmetic elective surgery¹
- Overdose of medication **without signs or symptoms**^{*2}
- The disease being treated or associated symptoms/signs unless more severe than expected for the patient's condition

¹ *Cosmetic elective surgery is cited here as example of an event that is not reportable as an AR*

² *Note that although overdose of medication without signs or symptoms may be excluded from AR reporting, it may still require investigation to ensure other protocol and regulatory requirements are met e.g. for IMP management and administration, or to ensure participant safety. If applicable, refer to appropriate part of Treatment section 8.9 (Overdose).*

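### The named checks on suicidal ideation and psychosis all fall after the 14-day course; the protocol names none before treatment or during it (minor)

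*Protocol*

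**What the plan says.** - **The check.** Section 10.7 places the same sentence under follow-up 1 (4-6 weeks after surgery) and follow-up 2 (12 weeks, plus or minus 4): "Checks on suicidal ideation and psychosis should be made and managed clinically as per routine practice". Follow-ups 3, 4 and 5 do not mention it, and the Schedule of Assessments has no row for it. Section 18.1 records that the text was added at these two visits in version 2.0, after the combined regulatory and ethics review.
- **Dosing.** Section 8.4: "The participant will take the medication for 14 days in total". The first dosing day is the day before surgery and the second is the day of surgery.
- **Baseline.** Section 10.4 lists history, performance status, EQ-5D-5L, resource use and driving licence status, and adds: "Presenting symptoms of specific interest will be collected". It does not name suicidal ideation or psychosis, and neither do the eligibility criteria in section 7. Section 10.5 places this contact "either at the pre-admission visit or on the ward as an in-patient, typically within 2 weeks of surgery".
- **On treatment.** The Schedule row "Recording of Serious Adverse Reactions" is marked in the dosing column and in the column that runs to 48 hours after the start of surgery. Section 12.6: "Active monitoring of safety events experienced by trial participants will be from the period of randomisation until completion of IMP course, plus 1 week".
- **Stopping.** Section 10.8 allows a clinician to stop treatment for a change in the participant's "condition that justifies the discontinuation of treatment".
- **Recording.** Under section 12.6, symptoms present at baseline are recorded if they worsen after treatment; pre-existing conditions that do not worsen are not.
- **Symptoms checklist.** Under Safety Assessments in section 10.7, a nurse administers it at follow-up 1. Its contents are not shown.

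**The concern.** The protocol treats these two symptoms as worth a named check in every participant, and section 5.2 lists mood disturbance among the side effects of levetiracetam, there in the context of long-term use. A check of this kind has two natural uses while a drug is under test. It can prompt the clinician to stop the drug, and it can show whether a symptom was there before the drug was started. The timing in section 10.7 serves neither use for the trial course.

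At stake are participant safety and clean attribution of the events that section 12 collects, namely serious adverse reactions and suspected unexpected serious adverse reactions. Safety of the drug is a stated secondary objective. The efficacy analysis is not involved.

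**Working it through.** **Inputs.** Course of 14 days from the day before surgery (sections 3 and 8.4). Bottles of 2 and 12 days (section 8.4). Follow-up windows (section 10.7). Active monitoring to one week past the end of the course (section 12.6). Surgery is post-operative day 0.

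**1. Course length.** 2 + 12 = 14 days, as the protocol states.

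**2. Last scheduled dose.** Course day 1 is post-operative day -1, so course day 14 is -1 + 13 = post-operative day 12.

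**3. Interval from last dose to each named check.**

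| Visit | Window (post-operative day) | Minus 12 |
|---|---|---|
| Follow-up 1 | 4 × 7 = 28 to 6 × 7 = 42 | 16 to 30 days |
| Follow-up 2 | 8 × 7 = 56 to 16 × 7 = 112 | 44 to 100 days |

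**4. End of active monitoring.** 12 + 7 = post-operative day 19. Follow-up 1 comes 28 - 19 = 9 to 42 - 19 = 23 days later.

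**5. Where a check is named.**

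| Period | Named check | General cover in the protocol |
|---|---|---|
| Screening and baseline | None | Medical history; presenting symptoms of interest |
| Course (day -1 to day 12) | None | Recording of serious adverse reactions; active monitoring; contact card (12.12); reference to SmPC precautions (8.8) |
| Follow-up 1 and 2 | Yes, in the text of 10.7 only | Symptoms checklist at follow-up 1 |

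**6. Reach of a check during admission.** A check on post-operative day 2 (48 hours) falls on course day 4 of 14. The protocol gives no length of stay. If discharge is on post-operative day d, the course days after discharge number 12 - d: 10 for d = 2, 7 for d = 5, 2 for d = 10. These values of d are assumptions.

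**The case against.** The sentence in section 10.7 is a clinical prompt left to routine practice, not a trial measurement. On that view it is unfair to fault it for lacking a baseline value. Stopping the drug never depended on it, because other routes exist: recording of serious adverse reactions through the course, active monitoring to day 19, continued reporting of serious events after that, clinician discretion under section 10.8, emergency unblinding under section 8.10 and a contact card. History is taken at screening and baseline and may cover psychiatric illness. Section 5.3 calls the toxicity of a 14-day course small and says that most side effects come with longer use. The late checks also have their own purpose, for late symptoms and for participants put on an anti-epileptic drug after a seizure.

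Most of this stands, and it is why the point is minor. Two things remain. Recording of serious adverse reactions captures events already recognised as serious and related; it does not put a question to the participant. And a check that the protocol asks of everyone is timed so that its answer can neither affect the trial course nor be compared with a named earlier answer.

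A reader might go further and infer that participants are unmonitored on drug, or that no psychiatric information is taken before treatment. The documents do not support either. The general cover above is explicit, and the contents of the eCRF and the symptoms checklist are not shown. What can be said is that the protocol names no such check, not that none is made.

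**Conclusion.** The point holds as a minor one. The only named checks on suicidal ideation and psychosis come 16-30 and 44-100 days after the last scheduled dose, and none is named before treatment or during the course. A symptom first found at these visits comes too late for stopping the trial drug. If it was already present before treatment, sites must rely on general history or recall to apply section 12.6.

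The intervals assume that the course runs to schedule. A course prolonged by missed doses would have to overrun by 16 days to reach even the earliest follow-up 1 visit.

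The size of any harm cannot be stated, since the documents give no rate for these symptoms and expect few side effects. It would be wrong to infer that psychiatric events will be missed in any particular number, or that the trial's comparison is weakened: no endpoint, estimate or power changes.

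**What to change.** - Ask the same brief question at the existing baseline contact, before randomisation.
- Ask it once more during the surgical admission, as late as practical before discharge. A check tied to the 48-hour time point would reach only course day 4, and some participants may still be intubated then.
- Give the check its own row in the Schedule of Assessments, so that a site working from the table does not overlook it at any of the four contacts.
- Keep the checks at follow-up 1 and follow-up 2.
- If the answer is positive, note the date of onset. Leave management to routine practice, as now.

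**Cost.** One short question at two contacts that already take place, for up to 1004 participants, with no new visit or staff. A check now left to routine practice gains a small recording task. The fix is partial: course days after discharge would still have no scheduled check (2 to 10 of the 14, on the assumed discharge on day 10 to day 2), and general reporting and the contact card would continue to cover them.
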